7.1.1.10 Tumor Lysis Syndrome (TLS) Risk Assessment

At Screening, all study subjects will be assessed for risk of developing TLS. The risk of TLS is a continuum based on multiple factors, including comorbidities. Subjects at increased risk are defined as having at least one lesion > 10 cm; or at least one lesion > 5 cm and circulating lymphocytes > 25,000 cells/mm³ and/or have reduced renal function CrCl < 60 mL/min. The risk may decrease as tumor burden decreases with venetoclax treatment.

Blood chemistry (creatinine, uric acid, potassium, phosphorus, calcium, and albumin if available) assessments will be performed in all subjects within 72 hours prior to initiating venetoclax treatment.

Subjects with high tumor burden at baseline and/or CrCl < 60 mL/min will be hospitalized during the first 24-48 hours of treatment at the 20 mg (Week 1) and the 50 mg (Week 2) venetoclax dose. Blood chemistry (creatinine, uric acid, potassium, phosphorus, calcium, and albumin if available) should be monitored pre-dose and 4 ± 1 , 8 ± 1 , 12 ± 1 , 24 ± 2 and, as needed, 48 ± 2 hours after the venetoclax dose. (Hospitalization for subjects lacking immediate access to a

facility capable of correcting TLS promptly or for subjects who are otherwise considered at risk for TLS should be discussed with the medical monitor). For all other subjects, blood chemistry will be monitored pre-dose, 6-8 and 24±2 hours after the venetoclax dose at the 20 mg and the 50 mg dose levels.

During the remaining ramp-up weeks (weeks 3-5), for subjects at increased risk for TLS at baseline, blood chemistries will be monitored at pre-dose and 6-8 hours after each dose increase.

Appropriate venetoclax dosing and management of subjects throughout their study treatment is guided by their individual risk for developing TLS. Risk-based TLS prophylaxis and management measures are described in Section 5.3.2.2.

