Appendix G. Howard Criteria for Laboratory and Clinical TLS* (Howard et al, NEJM 2011)

Metabolic Abnormality	Criteria for Classification of Laboratory Tumor Lysis Syndrome	Criteria for Classification of Clinical Tumor Lysis Syndrome
Hyperuricemia	Uric acid $> 8.0 \text{ mg/dL}$ (475.8 µmol/liter) in adults or above the upper limit of the normal range for age in children	
Hyperphosphatemia	Phosphorus > 4.5 mg/dL (1.5 mmol/liter) in adults or > 6.5 mg/dL (2.1 mmol/liter) in children	
Hyperkalemia	Potassium > 6.0 mmol/liter	Cardiac dysrhythmia or sudden death probably or definitely caused by hyperkalemia
Hypocalcemia	Corrected calcium < 7.0 mg/dL (1.75 mmol/liter) or ionized calcium < 1.12 (0.3 mmol/liter)†	Cardiac dysrhythmia, sudden death, seizure, neuromuscular irritability (tetany, paresthesias, muscle twitching, carpopedal spasm, Trousseau's sign, Chvostek's sign, laryngospasm, or bronchospasm), hypotension, or heart failure probably or definitely caused by hypocalcemia
Acute kidney injury‡	Not applicable	Increase in the serum creatinine level of 0.3 mg/dL (26.5 µmol/liter) (or a single value > 1.5 times the upper limit of the age-appropriate normal range if no baseline creatinine measurement is available) or the presence of oliguria, defined as an average urine output of < 0.5 mL/kg/hr for 6 hr

^{*} In laboratory TLS, two or more metabolic abnormalities must be present during the same 24-hour period within 3 days before the start of therapy or up to 7 days afterward. Clinical TLS requires the presence of laboratory TLS plus an increased creatinine level, seizures, cardiac dysrhythmia, or death.

Note: Only post-dose laboratory assessments will be considered when applying Howard Criteria for laboratory and clinical TLS.

[†] The corrected calcium level in milligrams per deciliter = measured calcium level in milligrams per deciliter + 0.8 × (4 – albumin in grams per deciliter).

[‡] Acute kidney injury is defined as an increase in the creatinine level of at least 0.3 mg per deciliter (26.5 µmol per liter) or a period of oliguria lasting 6 hours or more. By definition, if acute kidney injury is present, the patient has clinical TLS. Data about acute kidney injury are from (Levin 2007).

FINAL

Appendix H. Recommendations for Initial Management of Electrolyte Abnormalities and Prevention of Tumor Lysis Syndrome (TLS)

Section 1: First Dose of Venetoclax or Dose Escalation

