Uric acid \geq 10 mg/dL (595 μ mol/L) OR Uric acid \geq 8.0 mg/dL (476 μ mol/L) with 25% increase and creatinine increase \geq 0.3 mg/dL (\geq 0.027mmol/L) from pre-dose level	 Administer rasburicase (0.2 mg/kg as an intravenous infusion over 30 minutes). When rasburicase is used, sodium bicarbonate should not be used as this may exacerbate calcium phosphate precipitation. Consult nephrology (or other acute dialysis service). Recheck potassium, phosphorus, uric acid, calcium and creatinine in 1 hour STAT. If uric acid < 8.0 mg/dL 1 hour later, repeat potassium, phosphorus, uric acid, calcium and creatinine 2 and 4 hours later, if no other evidence of tumor lysis.
Hypocalcemia	
Calcium ≤ 7.0 mg/dL (1.75 mmol/L) AND Patient symptomatic (eg, muscle cramps, hypotension, tetany, cardiac arrhythmias)	 Administer calcium gluconate 50 to 100 mg/kg IV slowly with ECG monitoring. Telemetry. Recheck potassium, phosphorus, uric acid, calcium and creatinine in 1 hour STAT. If calcium normalized 1 hour later, repeat potassium, phosphorus, uric acid, calcium and creatinine 2 and 4 hours later, if no other evidence of tumor lysis. Calculate corrected calcium and check ionized calcium if albumin low
Hyperphosphatemia	
Phosphorus \geq 5.0 mg/dL (1.615 mmol/L) with \geq 0.5 mg/dL (0.16 mmol/L) increase	 Administer a phosphate binder (e.g., aluminum hydroxide, calcium carbonate, sevelamer hydroxide, or lanthanum carbonate). Nephrology (or other acute dialysis service) notification (dialysis required for phosphorus ≥ 10 mg/dL). Recheck potassium, phosphorus, uric acid, calcium and creatinine in 1 hour STAT. If phosphorus < 5.0 mg/dL 1 hour later, repeat potassium, phosphorus, uric acid, calcium and creatinine 2 and 4 hours later, if no other evidence of tumor lysis.
Creatinine	
Increase ≥ 25% from baseline	 Start or increase rate of IV fluids. Recheck potassium, phosphorus, uric acid, calcium and creatinine in 1 to 2 hours STAT.

Section 2: Ongoing Dosing of Venetoclax

Management of electrolyte changes from last value at intervals > 24 hours after either the first dose or dose escalation (eg, 48 or 72 hours) are as below.

Note: If the patient is hospitalized, no additional venetoclax doses should be administered until resolution.

- FINAL
- For potassium, admit patient for any increase $\geq 1.0 \text{ mmol/L } (1.0 \text{ mEq/L})$, or any level > upper limit of normal.

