The following safety analyses will be conducted to evaluate the use of venetoclax:

- Infectious pneumonia.
- TLS evaluated by adverse events of special interest and laboratory TLS per Howard criteria.
- Liver function abnormalities evaluated by laboratory data per Hy's law.
- GI Toxicities: No pooling will be done for diarrhea, nausea, and vomiting.
 - For each of the three preferred terms, events leading to treatment discontinuation and dose modification (dose reduction and/or dose hold) will be summarized.

 Table 3
 Summary of Safety Assessments

Assessment Type		
AE	TEAEs, SAEs, Grade 3 or higher TEAEs, related TEAEs, TEAEs leading to treatment discontinuation, TEAEs leading to dose reduction or dose hold, TEAEs leading to death, protocol-defined events of special interest defined by SMQ terms and other safety observations	Descriptive summary statistics and/or listings
Laboratory Parameters	Worst post-baseline toxicity grade for CTCAE-gradable hematology and chemistry results. Abnormalities in creatinine clearance, uric acid levels, and liver function tests. Laboratory TLS per Howard Criteria	Descriptive summary statistics and/or listings
Vital Signs and other Observations Related to Safety	Blood pressure, heart rate, temperature, and body weight, new or worsened eye-related symptoms	Descriptive summary statistics and/or listings

AE: adverse event; CTCAE: Common Terminology Criteria for Adverse Events; SAE: serious adverse event; TEAE: treatment-emergent adverse event; SMQ: standardized MedDRA (Medical Dictionary for Regulatory Activities) query.

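### The ionized-calcium cut-off for laboratory TLS lacks a unit and does not match the corrected-calcium cut-off on either reading, and the albumin that the corrected route needs is required inconsistently

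*Protocol*

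**What the plan says.** **The definition.** For laboratory TLS, Appendix G of the protocol says that "two or more metabolic abnormalities must be present during the same 24-hour period". The four candidates are uric acid, phosphorus, potassium and calcium. The calcium entry is "Corrected calcium < 7.0 mg/dL (1.75 mmol/liter) or ionized calcium < 1.12 (0.3 mmol/liter". Its second route, "or ionized calcium < 1.12 (0.3 mmol/liter", has no unit on the leading number. A footnote gives corrected calcium as "measured calcium level in milligrams per deciliter + 0.8 × (4 – albumin in grams per deciliter". Only post-dose results count.

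**Albumin.** Section 7.1.1.10 says, for the assessment before venetoclax starts: "Blood chemistry (creatinine, uric acid, potassium, phosphorus, calcium, and albumin if available) assessments will be performed in all subjects". For hospitalized subjects the ramp-up draws are also conditional: "creatinine, uric acid, potassium, phosphorus, calcium, and albumin if available) should be monitored pre-dose". The same condition stands in Sections 5.3.2.2, 7.1.2.2 and 8.2.1.1 to 8.2.1.4, and in footnote o of both schedules (Appendices A and B). Footnote r of both schedules lists albumin in the chemistry panel without that condition. Its separate list of tests due before each venetoclax increase names calcium but not albumin.

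**Ionized calcium.** It is in none of the scheduled panels. It appears as a test in the symptomatic hypocalcemia row of Appendix H: "Calculate corrected calcium and check ionized calcium if albumin low".

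**Where the definition is used.** Protocol Section 3.1.1 builds the run-in TLS rules on it, adding that the event must persist beyond 72 hours. SAP Section 5 plans "TLS evaluated by adverse events of special interest and laboratory TLS per Howard criteria", and SAP Table 3 gives the output as descriptive statistics and/or listings. SAP Section 5 also says that laboratory data come from local laboratories and that all values are converted to SI units.

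**The concern.** Two routes joined by an or should identify roughly the same condition. Here the ionized route has a leading number without a unit, next to an SI figure that is far from the corrected-calcium cut-off on the same row. A programmer working in SI units must decide whether the threshold is 0.3 or 1.12 mmol/L, and the SAP does not say. The corrected route depends on an analyte that the protocol treats as optional in some places and routine in others.

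The calcium limb of laboratory TLS could therefore be missed or falsely met for reasons unrelated to the subject's state. TLS is an important identified risk of venetoclax (protocol Section 1.3.3.1). Its frequency is a secondary safety endpoint (Section 10.2.3), and the data monitoring committee reviews TLS data to decide whether hospitalization in ramp-up is still needed (Section 3.1.2; SAP Section 1.1.2). Appendix G also makes laboratory TLS a component of clinical TLS, so an error can carry forward.

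**Working it through.** **1. Do the table's other unit pairs convert?** Using standard conversion factors on the Appendix G entries:
- uric acid: 8.0 mg/dL × 59.48 = 475.8 µmol/L (printed 475.8)
- phosphorus: 4.5 mg/dL × 0.3229 = 1.45 mmol/L (printed 1.5)
- creatinine: 0.3 mg/dL × 88.4 = 26.5 µmol/L (printed 26.5)
- corrected calcium: 7.0 mg/dL ÷ 4.008 = 1.747 mmol/L (printed 1.75)

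All agree to rounding.

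**2. Ionized calcium under each candidate unit for 1.12.**

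| Unit assumed | In mmol/L | Against the printed 0.3 mmol/L | As a share of 1.75 mmol/L |
|---|---|---|---|
| mg/dL | 1.12 ÷ 4.008 = 0.28 | agrees to one decimal | 0.28/1.75 = 16%; 0.3/1.75 = 17% |
| mmol/L | 1.12 | 1.12/0.3 = 3.7 times larger | 1.12/1.75 = 64% |
| mEq/L | 1.12 ÷ 2 = 0.56 | does not reproduce | 0.56/1.75 = 32% |

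The mg/dL reading reproduces the printed pair. The two routes would then be equivalent only if ionized calcium were 16-17% of total calcium; on the mmol/L reading, only if it were 64%.

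**3. What each reading means on the total-calcium scale.** The documents give no ionized share, so 40-55% is assumed here.
- Ionized equivalent of the corrected cut-off: 1.75 × 0.40 = 0.70 to 1.75 × 0.55 = 0.96 mmol/L.
- Reading 0.28-0.3 mmol/L: from 0.28/0.55 × 4.008 = 2.0 to 0.3/0.40 × 4.008 = 3.0 mg/dL total.
- Reading 1.12 mmol/L: from 1.12/0.55 × 4.008 = 8.2 to 1.12/0.40 × 4.008 = 11.2 mg/dL total.

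The row's other cut-off is 7.0 mg/dL.

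**4. What a missing albumin does.** Setting corrected calcium to 7.0 gives measured calcium = 7.0 − 0.8 × (4 − albumin).

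| Albumin (g/dL) | 4.0 | 3.5 | 3.0 | 2.5 | 2.0 |
|---|---|---|---|---|---|
| Measured calcium at the cut-off (mg/dL) | 7.0 | 6.6 | 6.2 | 5.8 | 5.4 |

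A measured 6.9 mg/dL at albumin 3.0 corrects to 6.9 + 0.8 × 1.0 = 7.7, so it is abnormal uncorrected and not met when corrected. Using uncorrected values over-calls hypocalcemia when albumin is below 4 g/dL. Treating a value without albumin as not met under-calls it. Neither convention is stated.

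**5. Albumin passages side by side.** Section 7.1.2.2 makes albumin conditional in the chemistry panel; footnote r lists it in that panel without condition. Sections 8.2.1.1 to 8.2.1.4 and footnote o keep it conditional at the dedicated TLS draws. The urgent rechecks in Appendix H name potassium, phosphorus, uric acid, calcium and creatinine, without albumin.

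**6. How sensitive the run-in rule was to classification.** At assumed true laboratory-TLS rates of 10%, 15% and 20%, the binomial chance of 3 or more events in 12 increased-risk subjects is 0.11, 0.26 and 0.44. The documents do not say how often calcium decides a classification, so this shows sensitivity only, not an effect.

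**The case against.** The strongest reply is that little turns on this. The routes are alternatives, and the corrected route has a self-consistent cut-off and a printed formula. Laboratory TLS can be met by any two of uric acid, phosphorus and potassium. Appendix G elsewhere prints mg/dL before SI, so the mg/dL reading is the natural one, its arithmetic closes, and the SI figure has its unit. Ionized calcium is rarely drawn, so its cut-off can seldom decide anything. TLS is also captured through adverse events. All of this stands, and it limits the size of the point.

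A reader might go further in five ways that the documents do not support:
- **That the calcium limb cannot work.** It works whenever albumin is measured.
- **That the ionized cut-off is unusable on both readings.** The mg/dL reading can be programmed. Saying that it would almost never be met, or that the mmol/L reading is far too loose, rests on the assumed ionized share.
- **That albumin is optional throughout.** Footnote r lists it without condition, so the fault is a contradiction between passages.
- **That a formal randomized comparison is compromised.** Protocol Section 10.6 plans no formal safety testing, and the SAP output is descriptive.
- **That the run-in decision is open to doubt.** SAP Section 1.1.2 treats the ramp-up schedule as already determined, and nothing shows that calcium decided any case.

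The reply does not answer two things. A threshold at one sixth of its stated alternative is not a credible alternative, and no rule covers calcium without albumin.

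**Conclusion.** The point holds in limited form. The ionized-calcium cut-off has no unit on its leading number and does not match the corrected-calcium cut-off on either reading: 16-17% of it as mg/dL, or a 3.7-fold contradiction of the printed SI figure as mmol/L. That much is arithmetic from the row itself. The translation to total calcium of about 2-3 or 8-11 mg/dL rests on the assumed 40-55% ionized share.

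The albumin passages contradict each other, and the plan gives no handling rule when albumin is absent. Only the calcium limb can be misclassified, and the documents do not allow the number of affected subjects to be estimated. The consequences still open are the SAP's laboratory TLS summary and any committee review based on the same derivation. Which ionized value was intended cannot be settled without the cited source. The correction is small and worth making before unblinding.

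**What to change.** 1. Check the ionized-calcium cut-off against the source cited in Appendix G and print one value with one unit. Alternatively, leave the ionized route out of the SAP derivation of laboratory TLS and say so. Appendix G also bears on withholding of venetoclax, so any change to the protocol definition itself is for the sponsor to reconcile clinically; no cut-off is proposed here.
2. Reconcile Sections 5.3.2.2, 7.1.1.10, 7.1.2.2 and 8.2.1.1 to 8.2.1.4 and footnote o with footnote r, so that albumin is reported with calcium on the TLS draws.
3. State in the SAP how a calcium value without same-sample albumin is classified, for example by using the nearest available albumin, with a sensitivity listing of subjects whose status depends on that choice.

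The cost is one more analyte on samples already drawn, a few lines of text and a small programming change. Data already collected without albumin cannot be repaired; only the SAP rule in item 3 can deal with them.

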Among the 106 subjects with relapsed/refractory NHL enrolled in the M12-175 study, 2 cases (1.9%) of laboratory TLS were observed during the Ramp-up Period at the 200 mg and 300 mg dose levels in subjects with bulky disease (tumor > 10 cm) with MCL (n=28) and DLBCL (n=41), respectively. To mitigate the risk of TLS observed in Cohort 1 in study M12-175, a Ramp-up Schedule of 3-4 weeks was used for subsequent cohorts.

The concurrent administration of ibrutinib and venetoclax in subjects at increased risk of TLS has not been investigated. In an ongoing dose-escalation study in subjects with relapsed/ refractory MCL (Portell 2016), the concurrent administration of 420 mg of ibrutinib and 400 mg of venetoclax to subjects with low/intermediate risk for TLS observed no cases of TLS, despite the fact that the ramp-up started at 100 mg of venetoclax and was only of 3 weeks duration (100, 200 and 400 mg). In the AIM MCL study, 560 mg of ibrutinib was administered 4 weeks prior to the administration of venetoclax. This was based on the rationale that the ibrutinib lead-in will reduce the risk of TLS. However, some subjects with high tumor burden did not respond to the ibrutinib lead-in and initiated venetoclax with increased, rather than reduced, tumor burden (Tam 2016). Therefore, given that the frequency of TLS in the setting of MCL has been reported to be low and to prevent early progression with single-agent ibrutinib, the concomitant administration of ibrutinib and venetoclax is warranted to initially evaluate the safety profile for the combination.

During the Safety Run-in Period, 12 subjects at increased risk for TLS (ie, subjects with high tumor burden and/or baseline creatinine clearance [CrCl] < 60 mL/min) and 6-9 subjects at low risk for TLS (not meeting these criteria) will receive ibrutinib at 560 mg plus venetoclax starting at 20 mg and ramped-up to a target dose of 400 mg over a 5-week period.

Depending on the number of TLS events and DLTs in each of the TLS risk categories, the Randomization Phase will start with either the concurrent administration of ibrutinib and venetoclax using the 5-week standard Ramp-up Schedule (see Section 3) or with a 4-week ibrutinib lead-in followed by the initiation of venetoclax using the 5-week standard Ramp-up Schedule.

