3.1.1 Safety Run-in Period

The study will start with an open-label Safety Run-in Period to evaluate the occurrence of TLS and DLTs with the concurrent administration of ibrutinib and venetoclax. TLS and DLT occurrence will be assessed during the venetoclax Ramp-up Period for a minimum of 5 weeks.

Up to 27 subjects may be enrolled during the Safety Run-in Period (Figure 6).

Figure 6. Study Schematic – Safety Run-in Period

PD = progressive disease; WC = withdrawal of consent

Tumor Lysis Syndrome (TLS) Categories

Two TLS risk categories will be evaluated separately and in parallel:

- Increased risk for TLS Subjects with high tumor burden (at least one lesion > 10 cm; or at least one lesion > 5 cm and circulating lymphocytes > 25,000 cells/mm³) and/or with baseline creatinine clearance (CrCl) < 60 mL/min. During the Safety Run-in Period, subjects at increased risk for TLS will be hospitalized for a minimum of 24 hours (and up to 48 hours at the discretion of the investigator) at the start of the 20 mg ramp-up dose and again at the start of the 50 mg ramp-up dose of venetoclax for monitoring and prophylaxis of TLS.
- Low risk for TLS Subjects not meeting the criteria described above.

TLS events are defined as follows:

- Clinical TLS any event that meets Howard criteria (Appendix G) with the following exceptions:
 - For the purpose of TLS assessment during the Safety Run-in Period, only those increases in serum creatinine > 1.0 mg/dL from pre-treatment baseline will be considered clinical TLS.
 - In subjects with renal dysfunction at baseline (CrCl < 60 mL/min), clinical TLS is defined as the presence of laboratory TLS plus either seizures, cardiac dysrhythmia, or death.
- Laboratory TLS any event that meets Howard criteria (Appendix G) for laboratory TLS, that does not resolve within 72 hours despite protocol required management.

Dose-Limiting Toxicity (DLT)

A DLT is defined as any Grade 3 or higher non-TLS AE at least possibly related to study drug (ibrutinib and/or venetoclax) and occurring during the DLT assessment period with the following clarifications:

Non-Hematologic DLTs:

[figure not shown]
- Grade ≥ 3 nausea, vomiting or diarrhea uncontrolled despite maximum medical supportive care and persisting > 5 days
- Grade 3 fatigue persisting > 7 days
- Grade 3 infection is not a DLT, however an infection with life-threatening consequences or requiring urgent intervention (Grade 4) will be considered a DLT

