5.3.2.2 Venetoclax Toxicity Management

Prophylaxis and Management of Tumor Lysis Syndrome

Venetoclax can cause rapid reduction in tumor and thus poses a risk for TLS in the Ramp-up Period. Changes in electrolytes consistent with TLS that require prompt management can occur as early as 6-8 hours following the first dose of venetoclax and at each dose increase. The risk of TLS is a continuum based on multiple factors, including comorbidities. Subjects with high tumor burden are at a greater risk of TLS when initiating venetoclax. Reduced renal function further increases the risk. The risk may decrease as tumor burden decreases with venetoclax treatment.

Tumor burden assessments, including radiographic evaluation (eg, CT scan) should be performed at Screening as well as blood chemistry assessments (creatinine, uric acid, potassium, phosphorus, calcium, and albumin, if available) in all subjects. Pre-existing abnormalities should be corrected prior to initiation of treatment with venetoclax.

The prophylaxis measures listed below should be followed and more intensive measures (including hospitalization) should be employed as overall risk increases:

Hydration: Ensure adequate hydration (1.5-2 L) 48 hours prior to initiating therapy with venetoclax and throughout the Ramp-up Period, especially on the first day of each ramp-up dose. Administer intravenous (IV) fluids as indicated based on overall risk of TLS or for those who cannot maintain adequate oral hydration.

Anti-hyperuricemic agents: Administer allopurinol within 72 hours prior to initiation of venetoclax; consider continuing through the Ramp-up Period. Rasburicase is recommended for subjects at high risk, especially those with high tumor burden.

Laboratory Assessments:

Pre-dose: Assess blood chemistries prior to initiating venetoclax to evaluate kidney function and correct pre-existing abnormalities. Reassess blood chemistries before starting each subsequent ramp-up dose of venetoclax.

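### Appendix G's 7-day limit on laboratory TLS contradicts the 5-week TLS assessment period; read literally, it excludes the 100, 200 and 400 mg steps

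*Protocol*

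**What the plan says.** **The definition.** Protocol Section 3.1.1 defines laboratory TLS in the run-in as "any event that meets Howard criteria (Appendix G) for laboratory TLS, that does not resolve within 72 hours despite protocol required management". It takes clinical TLS from the same appendix with two exceptions. A creatinine rise counts only above 1.0 mg/dL over the pre-treatment baseline. With baseline CrCl below 60 mL/min, laboratory TLS plus a seizure, dysrhythmia or death is needed.

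The first footnote of Appendix G says that two or more abnormalities "must be present during the same 24-hour period within 3 days before the start of therapy or up to 7 days afterward". It continues: "Clinical TLS requires the presence of laboratory TLS plus an increased creatinine level, seizures, cardiac dysrhythmia, or death". A note adds: "Only post-dose laboratory assessments will be considered when applying Howard Criteria for laboratory and clinical TLS". The footnote on acute kidney injury says something different: such injury alone makes the patient a clinical TLS case.

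**The assessment period.** Section 3.1.1 says "TLS and DLT occurrence will be assessed during the venetoclax Ramp-up Period for a minimum of 5 weeks". SAP Section 2 also sets the TLS/DLT assessment period as the standard ramp-up, at least 5 weeks long. Section 5.3.2.2 says that electrolyte changes consistent with TLS "can occur as early as 6-8 hours following the first dose of venetoclax and at each dose increase", and Section 1.3.3.1 places the risk in the first 5 weeks of ramp-up.

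**The analysis.** SAP Section 5 lists "TLS evaluated by adverse events of special interest and laboratory TLS per Howard criteria", and its Table 3 repeats the laboratory item. Neither gives a time window for the Howard derivation.

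**The concern.** The Howard criteria assume one start of therapy. This regimen has five weekly venetoclax dose levels, and the protocol recognises TLS risk at each. The sponsor adapted the criteria in several respects (72-hour persistence, the creatinine threshold, the rule for renal dysfunction, post-dose samples only) but left the single 7-day limit in place.

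Two outputs use the definition. TLS occurrence is part of the run-in's primary objective, and the count of laboratory TLS events feeds the rules in Section 3.1.1 that choose the ramp-up for randomization. TLS frequency is also a secondary safety objective of the randomized phase, where the SAP derives laboratory TLS from the chemistry data. A programmer who follows Appendix G as printed and one who follows the 5-week assessment period could report different counts from the same data. A low count under the first reading could come from the definition rather than from a safe ramp-up.

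**Working it through.** **Inputs.** The dose levels are 20, 50, 100, 200 and 400 mg, one week each (Protocol Appendix A; SAP Section 3.4). Ibrutinib and venetoclax/placebo both start on Week 1 Day 1. The window is 7 days after the start of therapy (Appendix G).

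**Check of the weekly steps.** The SAP's planned dose intensity reproduces from them:

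(20 + 50 + 100 + 200 + 400) × 7 = 5,390 mg

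400 × (728 − 35) = 277,200 mg

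(5,390 + 277,200) / 728 = 388.2 mg/day, as printed.

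**Step days against the window.** Week w Day 1 is study day 7(w − 1) + 1. The window closes on Day 1 + 7 = Day 8.

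| Level | First day | Days after start | Inside window? |
|---|---|---|---|
| 20 mg | 1 | 0 | yes |
| 50 mg | 8 | 7 | Day 8 only |
| 100 mg | 15 | 14 | no |
| 200 mg | 22 | 21 | no |
| 400 mg | 29 | 28 | no |

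At 50 mg, the draws at 24 hours (Day 9) and, where needed, 48 hours (Day 10) already fall outside. The window covers 8 of 35 ramp-up days: 8/35 = 23%.

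**With the window restarted at each level.** The windows are Days 1–8, 8–15, 15–22, 22–29 and 29–36. Together they cover all 35 days.

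**Illustration for the run-in rules.** The rates here are assumptions; the documents give no TLS risk by step. Let p be the per-subject probability of laboratory TLS over the full ramp-up, f the share of it that falls inside the window, and q = p × f. Clinical events are ignored.

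- Increased risk: the rule is triggered by 3 or more of 12, with probability P(X ≥ 3), X ~ Bin(12, q).
- Low risk: the rule is triggered by 2 or more of 6, or by 1 of 6 followed by at least 1 of 3 more, with probability P(X ≥ 2), X ~ Bin(6, q), plus 6q(1 − q)⁵ × [1 − (1 − q)³].

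For p = 25%:

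| f | q | Increased-risk rule | Low-risk rule |
|---|---|---|---|
| 100% | 25% | 0.61 | 0.67 |
| 60% | 15% | 0.26 | 0.38 |
| 40% | 10% | 0.11 | 0.21 |
| 20% | 5% | 0.02 | 0.07 |

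Over p from 10% to 40%, the increased-risk rule is triggered with probability 0.11 to 0.92 if all steps count, and 0.01 to 0.30 if f = 40%. For the low-risk rule the ranges are 0.21 to 0.91 and 0.04 to 0.41.

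**The case against.** The strongest reply is that the intent is plain. The 5-week assessment period is stated repeatedly in the protocol and again in SAP Section 2, and SAP methods take precedence over the protocol's. Chemistry is scheduled after the 100, 200 and 400 mg steps for increased-risk subjects. On this view the 7 days are text carried over from a published criterion that nobody would apply literally. That stands as evidence of intent. It does not settle the derivation, because the SAP points back to the Howard criteria and no text says that the 7 days restart.

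Four stronger readings might be inferred, and the documents do not support them.

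- *Late TLS goes unreported.* SAP Section 5 also summarizes TLS as an adverse event by narrow SMQ over the treatment-emergent period, with no 7-day limit. Only the laboratory derivation is exposed.
- *Late clinical TLS cannot count.* The kidney-injury footnote offers a route that needs no laboratory TLS. It conflicts with the first footnote, and Section 3.1.1 closes that route for subjects with CrCl below 60 mL/min.
- *The monotherapy study shows that TLS comes late.* Its two cases of "laboratory TLS were observed during the Ramp-up Period at the 200 mg and 300 mg dose levels" arose under a different regimen, and no time since first dose is given.
- *Only 23% of the TLS risk is captured.* The 23% is a share of days. Section 5.3.2.2 says that risk may fall as tumor burden falls, so the early steps may carry more than a proportionate share.

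**Conclusion.** The contradiction is real and should be resolved before unblinding. As printed, Appendix G stops counting laboratory TLS on Day 8, while the protocol and SAP assess TLS through a ramp-up of at least 35 days. Three of the five dose levels fall wholly outside the window, and the 50 mg level falls outside after its first day. Clinical TLS is affected where it depends on laboratory TLS: under the first Appendix G footnote, and under Section 3.1.1 for CrCl below 60 mL/min.

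This rests on the literal wording, with therapy starting on Day 1 and no repeated level. The probabilities under the run-in rules are illustrations at assumed rates. A reader might infer that events were missed or that the ramp-up was wrongly chosen; the documents show neither. SAP Section 1.1.2 records that the standard ramp-up without an ibrutinib lead-in has already been judged appropriate, and the documents do not say how the run-in events were counted. PFS, its significance level and its power are not affected.

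**What to change.** Reconcile Protocol Section 3.1.1 and Appendix G with SAP Section 2, Section 5 and Table 3:

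- State in Appendix G and in SAP Section 5 and Table 3 that the 7-day window applies after the first dose at each venetoclax/placebo level, including a restarted level, through 7 days after the first 400 mg dose. By Appendix G's counting that is Day 36, whereas SAP Section 2 ends the DLT period on the 7th day at 400 mg, which is Day 35. State which applies.
- Keep the absolute metabolic thresholds and the pre-treatment creatinine baseline of Section 3.1.1. A new reference value at each step would contradict that baseline and could hide a cumulative rise.
- Resolve the two Appendix G footnotes on whether clinical TLS requires laboratory TLS.
- Use one derivation for the run-in and both randomized arms. Report the run-in counts on this basis as confirmation of the decision already taken.
- State a data limitation. Section 7.1.1.10 and the TLS footnote of Appendix A schedule post-dose chemistry at 100 to 400 mg for increased-risk subjects only, while Section 5.3.2.2 carries the same monitoring to every step. These passages must be reconciled, and late-step data for low-risk subjects may be incomplete.

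The cost is a few sentences, a small programming change and possibly a higher reported TLS count. The change alters an endpoint derivation, not patient management.
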